7.3.2 Clinical/symptom assessment

A clinical assessment including vital signs (heart rate, systolic and diastolic BP, oxygen saturation (pulse oximetry), and temperature will be performed at:

- Cycles 1-2 (days 1 and 15)
- Cycles 3 onward (day 1 of every cycle)
- End of Treatment Visit,
- 30 day Follow-up Visit.

Constitutional symptoms will be collected during cycles 1-2 (day 1 and 15), cycle 3 onwards (day 1), and End of Treatment Visit.

Constitutional symptoms will include the, night sweats, weight loss and recurrent fever ≥38.0°C in the absence of infection,.

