7.5 Dose Modifications

AZD2014 is expected to be well tolerated. Substantial toxicities should be managed as medically indicated and with temporary suspension of study drug, as appropriate. Dose reductions or holds and initiation of supportive care are allowed as clinically indicated by the treating physician. For each patient, a maximum of two dose reductions will be allowed. The reduced dose levels are presented in Table 1. If patients are unable to tolerate the 75mg bd dose of AZD2014, there is a possibility of changing to a continuous dosing regimen which may in some cases be better tolerated. This needs to be discussed with the chief investigator on a case by case basis.

Table 1.	AZD2014 dose level modification	
Dose level	AZD2014 PO daily dose	
Starting Dose	125 mg bd	
-1 Dose Level	100 mg bd	
-2 Dose Level	75 mg bd	

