7.5.1 General dose modifications for toxicities

Dose reduction and discontinuation guidelines for haematologic and non-haematologic toxicities due to AZD2014 are shown in Table 2 and 3. Dose re-escalation is not permitted.

Table 2.	Dose modifications and discontinuation criteria for non-haematologic toxicities*

NCI CTCAE Toxicity Grade	Action
Grade 1, or 2	None
Grade 3 or 4 and/or clinically significant	
Expected manageable/reversible with dose reduction	Hold study drug until meets one of the criteria below:
Toxicity remains (despite dose interruption) grade 3 or 4 or is clinically significant > 14 days	Discontinue study drug
Toxicity lasts 14 days or less and resolves to grade 2 or less or is no longer clinically significant	Reduce dose level per Table 1 and restart once toxicity has resolved to grade 2 or less or is no longer clinically significant
Grade 3 or 4 and/or clinically significant	
Not expected to be manageable/reversible with dose reduction	Discontinue study drug
Recurrence of Grade 3	Reduce one more dose level is available (see table 1), or if not discontinue study drug. NB note option of continuous dosing schedule as mentioned in 7.5

 Table 2.
 Dose modifications and discontinuation criteria for non-haematologic toxicities*

NCI CTCAE Toxicity Grade Action	
Recurrence of Grade 3 cardiac event ^a	Discontinue study drug
Recurrence of Grade 4	Discontinue study drug

* If the below specific recommendations for stomatitis/oral mucositis, hyperglycaemia, ILD/pneumonitis, ECG-changes and rash disagree with table 2 please follow the below not recommendations not table 2.

	Table 3.	Dose modifications and discontinuation criteria for haematological toxicitie
--	----------	--

NCI CTCAE toxicity grade	Action
Thrombocytopenia	
Grade 1, 2 or 3 (without bleeding)	None
Grade 3 (with bleeding) or grade 4	Hold study drug until it meets one of the criteria below:
Toxicity remains (despite dose interruption) grade 3 (with on-going bleeding episodes) or 4 > 14 days	Discontinue study drug
Toxicity lasts 14 days or less and resolves to grade 2 or less	Reduce dose level per table 1 and restart once toxicity has resolved to grade 2 or less
Neutropenia (NB GCSF is permitted as per local p	olicy)
Grade 1, 2 or 3	None
Grade 4	Hold study drug until it meets one of the criteria below:
Toxicity remains (despite dose interruption and GCSF) grade 4 > 14 days	Discontinue study drug

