7.5.2.2 Recommendation for Treatment of Stomatitis/Oral Mucositis/Mouth Ulcers

For mild toxicity (Grade 1), use conservative measures such as non-alcoholic mouth wash or salt water (0.9%) mouth wash several times immediately after drug administration (1-3h) and during the day as required until resolution. AZD2014 treatment can be continued without a dose reduction.

For more severe toxicity (Grade 2 or 3), the suggested treatments are topical analgesic mouth treatments (i.e., local anesthetics such as benzocaine, butyl aminobenzoate, tetracaine hydrochloride, menthol, or phenol), with or without topical corticosteroids, such as triamcinolone oral paste 0.1% (e.g., Kenalog in Orabase®). Opioid analgesia (either intravenous, subcutaneous, or oral) is permitted. AZD2014 should be stopped until stomatitis improves to \leq Grade 1, and then resumed without a dose reduction. If Grade 2 to 3 stomatitis recurs, dose reduce AZD2014

Agents containing hydrogen peroxide, iodine, and thyme derivatives may worsen mouth ulcers. It is preferable to avoid these agents.

If the toxicity resolves or reverts to \leq CTCAE Grade 2 within 14 days of onset and the patient is showing clinical benefit, treatment with AZD2014 may be restarted, at the same dose or a lower dose, at the discretion of the Investigator.

If the toxicity does not resolve to \leq CTCAE Grade 2 after 14 days, then the patient should be withdrawn from the study and observed until resolution of the toxicity.

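### Section 7.5.2.2 gives two unreconciled restart rules for stomatitis, so a grade 3 event that has fallen to grade 2 may be held or redosed

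*Protocol*

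**What the plan says.** All of this is in the Protocol.

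- **Section 7.5.2.2, second paragraph (grade 2 or 3).** AZD2014 is stopped until stomatitis is at most "Grade 1, and then resumed without a dose reduction". The dose is reduced only if grade 2 to 3 stomatitis recurs.
- **Section 7.5.2.2, fourth paragraph.** If the toxicity comes down to at most "CTCAE Grade 2 within 14 days of onset and the patient is showing clinical benefit", then "treatment with AZD2014 may be restarted, at the same dose or a lower dose, at the discretion of the Investigator".
- **Section 7.5.2.2, fifth paragraph.** If the toxicity is still above grade 2 after 14 days, "then the patient should be withdrawn from the study and observed until resolution of the toxicity".
- **Section 7.5.1, Table 2.** For the row "Toxicity remains (despite dose interruption) grade 3 or 4 or is clinically significant > 14 days" the action is to discontinue study drug. The footnote covers disagreement between the specific recommendations, stomatitis among them, and the table: "please follow the below not recommendations not table 2".
- **Section 7.5.** "Dose reductions or holds and initiation of supportive care are allowed as clinically indicated by the treating physician". No restart grade is given there.
- **Section 1.2.3.2.** Mucositis is listed among the most frequently reported events, which were also those of highest severity and those most often leading to interruption or permanent discontinuation.

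**The concern.** The two restart paragraphs use different grade thresholds for what can be the same event, and neither refers to the other. A site following the second paragraph keeps a patient off drug at grade 2. A site following the fourth may redose that patient through grade 2 mucositis. Both comply.

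The first thing at stake is patient safety and uniform dosing across a multicentre trial, for a toxicity the protocol itself describes as frequent and often dose-limiting. There is a possible second effect: Section 12.6 counts a patient as not tolerating treatment if toxicity leads to a delay or dose modification in the first two cycles. Which paragraph a site follows could therefore sometimes decide how a patient is counted.

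**Working it through.** The protocol states no figure on this point, so the check is a comparison of text, with some calendar arithmetic.

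**Step 1. Apply both paragraphs to each case.**

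| Case | Second paragraph | Fourth paragraph | Result |
|---|---|---|---|
| Grade 3, now grade 2, within 14 days of onset, clinical benefit | Stay off drug | May restart, same or lower dose | Direct conflict |
| Grade 3, now grade 1 or less, within 14 days, clinical benefit | Resume at same dose | Same or lower dose | Soft conflict: only the optional lower dose differs |
| Grade 2 throughout | Stop | Wording supposes toxicity that has come down and drug already interrupted | Second paragraph governs on the natural reading |
| Grade 3, now grade 2, no clinical benefit | Stay off drug | Condition not met | No conflict |

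**Step 2. Look for a tie-breaker.** The Table 2 footnote ranks Section 7.5.2.2 above Table 2, which sends the reader back to the section containing the conflict. Section 7.5 permits holds and reductions but sets no restart grade. The fourth paragraph is not confined to grade 4, to recurrence or to any other setting. Sections 7.7 and 7.9 do not address restart after stomatitis. Nothing settles it.

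**Step 3. A dated example.** Section 7.2 doses on days 1, 2, 8, 9, 15, 16, 22 and 23 of each 28-day cycle. Suppose grade 3 stomatitis starts on cycle 2 day 24 and is grade 2 at the scheduled visit on cycle 3 day 1. Suppose also that the investigator judges there is clinical benefit.
- Onset: 28 + 24 = study day 52.
- Next dosing day: 2 × 28 + 1 = study day 57.
- Time since onset: 57 − 52 = 5 days, inside the 14-day limit.
- Second paragraph: both dosing days are omitted, so 0 mg that week.
- Fourth paragraph at the same dose: 2 days × 2 doses × 125 mg = 500 mg that week.

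**Step 4. How far this reaches into the Section 12.6 window.** The first days of the weekly dosing pairs after the initial pair, in cycles 1–2, are study days 8, 15, 22, 29, 36, 43 and 50, seven in all. The earliest scheduled on-treatment scan is the PET-CT on days 17–21 of cycle 2, that is 28 + 17 = 45 to 28 + 21 = 49. If clinical benefit must be shown by a scheduled scan, only day 50 qualifies, one of seven. If the investigator may judge benefit clinically, all seven could. Section 7.5.2.2 does not define the term.

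**Step 5. The exit.** The fifth paragraph acts only above grade 2. Under the second paragraph alone, a patient still at grade 2 after 14 days may not restart and has no stated exit. The fifth paragraph also removes the patient from the study where Table 2 discontinues drug. Sections 7.9 and 7.10 provide follow-up after treatment stops, so this last difference is one of wording.

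**The case against.** **The fourth paragraph may be a permissive exception, or may be meant for grade 4 or recurrent events.** The text says neither. As an exception it would permit exactly the redosing at grade 2 that the second paragraph forbids. Confined to grade 4, it would let a worse event restart at a higher residual grade than a grade 2 or 3 event.

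**These are only recommendations.** The footnote nevertheless tells sites to follow them in place of Table 2.

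**The dose difference is slight.** This stands. The fourth paragraph permits the second paragraph's dose, and Section 7.5 already allows a clinically indicated reduction. The restart grade carries the point.

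**A reader might infer that every grade 2 event meets the fourth paragraph's threshold at onset, when the second says stop.** The wording does not support this. It speaks of toxicity resolving or reverting and of drug being restarted, which supposes an event that was above grade 2 and an interruption.

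**A reader might infer that the Section 12.6 tolerability decision is materially distorted.** The documents do not support this either. The clinical-benefit condition is hard to meet before the first scans, and a patient who misses a dose under both paragraphs is counted the same way. Recoding a few patients and recomputing the design's error rates would add nothing: the number recoded would be arbitrary, the shifts could go either way, and any other cause of recoding would give the same figures. Tolerability is also a secondary outcome, and Section 12.4 makes the interim rule guidance only.

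**Conclusion.** The contradiction is real and confined to one subsection. Its clear case is grade 3 stomatitis that has fallen to grade 2 within 14 days in a patient judged to be benefiting. There, the same event can mean a full week's drug (500 mg) or none, and no other provision decides between them.

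The number of patients affected is unknown because the protocol gives no stomatitis rate. Section 1.2.3.2 indicates that mucositis is common with this drug, but does not give its frequency on the intermittent schedule used here. The consequence is mainly for dosing safety and consistency between sites. An effect on the tolerability count is possible but unquantified. No effect on the primary response outcome has been shown. The conclusion rests on reading the fourth paragraph as applying to grade 3 events, which its wording allows and nothing else in the protocol excludes.

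**What to change.** Amend Section 7.5.2.2:

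1. Keep one restart rule for grade 2–3 stomatitis: stop AZD2014, resume at the same dose at grade 1 or less, and reduce one level on recurrence.
2. Delete the fourth paragraph, or limit it explicitly to a case the second paragraph does not cover, with one stated dose.
3. Align the 14-day exit with the kept threshold, so that a patient still at grade 2 after 14 days has a stated action. Without this, removing the fourth paragraph leaves that patient with neither a restart nor an exit rule.
4. Replace withdrawal from the study with discontinuation of study drug, follow-up continuing under Sections 7.9 and 7.10.

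This is a rewording of one subsection, with no extra data or visits. The downside is a few more missed doses for patients still at grade 2 on a dosing day. If the action chosen under item 3 is discontinuation, some patients with persistent grade 2 stomatitis would come off drug; that is a clinical choice for the sponsor, but it has to be written down.

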7.2 Treatment Schedule

AZD2014 is to be administered twice daily orally on an intermittent schedule at a dose of 125mg. Two consecutive days of treatment will be followed by 5 days with no treatment each week. Treatment would therefore be on days 1, 2, 8, 9, 15, 16, 22 and 23 of each cycle of 28 days. Treatment days should be two consecutive days and should be the same days each week, for example if treatment was started on a Monday in the first week further treatments would be expected to continue to be on Mondays and Tuesdays each week. Treatment will continue until progression or withdrawal due to toxicity or due to patient choice.

For the second, combination, stage of the trial, rituximab 375mg/m² will also be administered intravenously in the standard fashion as per local protocol on day 1 of the 28 day cycle for a total of 6 cycles. Pre-medication with antihistamines (e.g.Piriton), hydrocortisone and paracetamol is permissive as per local protocols for use of rituximab in the 6 patient combination stage.

Where possible all doses of AZD2014 should be taken at approximately the same times each day. AZD 2014 doses can be taken with or without food. Twice daily doses should be taken approximately 12 hours apart. If vomiting occurs within 30 minutes after AZD2014 dosing, or if the tablet(s) can be identified in the vomit content, the patient can re-take new tablet(s).

If a patient misses a dose and remembers within 2 hours, they should take the dose straight away and continue to take the rest of their medication as planned. If a dose is missed and the patient remembers after 2 hours or longer, they should take the next dose when it is due

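### Section 7.5.2.2 contradicts itself on restarting AZD2014 after Grade 3 stomatitis: one paragraph requires recovery to Grade 1 or less, another accepts Grade 2

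*Protocol*

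**What the plan says.** Paragraphs of Protocol section 7.5.2.2 are counted from its start, so the Grade 1 advice is paragraph 1 and the note on mouth agents to avoid is paragraph 3.

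- **Paragraph 2 (Grade 2 or 3).** "AZD2014 should be stopped until stomatitis improves to" at most "Grade 1, and then resumed without a dose reduction. If Grade 2 to 3 stomatitis recurs, dose reduce AZD2014".
- **Paragraph 4 (no starting grade given).** If the toxicity has come down to at most "CTCAE Grade 2 within 14 days of onset and the patient is showing clinical benefit", then "treatment with AZD2014 may be restarted, at the same dose or a lower dose, at the discretion of the Investigator".
- **Paragraph 5.** If the toxicity has not come down to at most "CTCAE Grade 2 after 14 days, then the patient should be withdrawn from the study".
- **Section 7.5.1, Table 2 (non-haematological toxicity in general).** After a Grade 3 or 4 event that recovers within 14 days: "Reduce dose level per Table 1 and restart once toxicity has resolved to grade 2 or less". The footnote says that where the "specific recommendations for stomatitis/oral mucositis, hyperglycaemia, ILD/pneumonitis, ECG-changes and rash disagree with table 2", the specific text is to be followed.
- **Section 7.2 (schedule).** "Two consecutive days of treatment will be followed by 5 days with no treatment each week".
- **Section 12.6 (tolerability).** A toxicity in the first 2 cycles that causes a treatment delay or dose modification counts as a non-tolerable outcome.

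**The concern.** Paragraphs 2 and 4 can both apply to the same patient on the same day and give different instructions. Two sites that each comply with the protocol could then treat identical events differently, one holding the drug and the other dosing through Grade 2 stomatitis.

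The dose chosen at restart has lasting consequences. Section 7.5 allows at most two reductions and section 7.5.1 forbids re-escalation.

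Section 1.2.3.2 lists mucositis among the most frequent adverse events and among those that most often led to interruption or discontinuation, so the rule is not a remote one. Because section 12.6 scores delays and dose modifications, the choice of paragraph can also decide whether an event counts against tolerability.

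**Working it through.** No stated figure is in dispute, so the check is a comparison of the texts followed by a trace through the schedule.

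**Step 1: do the two paragraphs overlap?** Paragraph 2 covers Grades 2 and 3. Paragraph 4 refers only to the toxicity. It does not confine itself to Grade 4, to first events or to recurrences, and does not call itself an exception to paragraph 2. A Grade 3 event that has improved falls under both.

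**Step 2: what does each text instruct?** The paragraph 4 column assumes clinical benefit and recovery within 14 days of onset.

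| Grade 3 event, current state | Paragraph 2 | Paragraph 4 | Table 2 |
|---|---|---|---|
| First event, now Grade 2 | Hold | May restart, same or lower dose | Restart one level lower |
| First event, now Grade 1 or less | Resume, same dose | May restart, same or lower dose | Restart one level lower |
| Recurrence, now Grade 2 | Hold | May restart, same or lower dose | Reduce a further level if one is available |
| Recurrence, now Grade 1 or less | Resume, reduced dose | May restart, same or lower dose | Reduce a further level if one is available |

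The recovery grade conflicts in rows 1 and 3. On dose, row 4 has paragraph 4 permitting the full dose where paragraph 2 reduces, and row 2 has it permitting a reduction where paragraph 2 has none.

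**Step 3: does another text break the tie?** Table 2 gives a third version, but its footnote defers to 7.5.2.2 where they disagree. The reader is sent back to the section that conflicts with itself.

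**Step 4: can the choice change a tolerability score?** Dosing blocks start on days 1, 8, 15 and 22. As an illustration, take a first Grade 3 event with onset on day 3 of cycle 1.

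- Still Grade 3 on day 8: both paragraphs hold. A delay is scored either way.
- Grade 2 on day 8: paragraph 2 omits the day 8 block, which is a delay and counts. Paragraph 4, if clinical benefit is judged present, allows the block on time at full dose, so nothing counts.
- Grade 1 or less on day 8: paragraph 2 gives the full dose on time, so nothing counts. Paragraph 4 gives the same score unless the investigator chooses a lower dose, which is a modification.

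The score can differ, but only on particular paths.

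**Step 5: how close are the thresholds?** Section 12.6 allows at most 5 such toxicities in the first 15 patients and 9 in 30. In the combination stage it allows 1 in the first 3 patients and 2 in 6. A single event scored differently could matter most in the combination stage. The protocol gives no rate of Grade 3 stomatitis, so the number of events on the conflicting paths cannot be derived.

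**The case against.** The best defence is that discretion is intended. Section 7.5 lets the treating physician reduce or hold as clinically indicated, 7.5.2.2 is headed as a recommendation, and paragraph 4 is permissive. It could be a deliberate exception for benefiting patients, or meant for Grade 4 events, which paragraph 2 does not cover. A site that always follows paragraph 2 breaches nothing. All of that is fair, but the text states neither limit, does not define clinical benefit, and leaves a site that follows paragraph 4 equally compliant.

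The defence is stronger on size. Section 1.2.3.2 says that most events were Grade 1 or 2 and that the common ones generally reversed within 1 week of stopping. If clinical benefit means imaging response, section 7.3.4 places the first on-treatment CT after 2 cycles, so paragraph 4 would rarely apply inside the tolerability window. Section 12.4 makes the 15-patient stopping rule guidance only. These points stand.

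Three stronger readings are tempting but not supported:

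- A reader might infer that a Grade 2 event meets paragraph 4 at onset. That strains the wording, which speaks of toxicity coming down to Grade 2 and of treatment being restarted. A Grade 2 event does not revert to Grade 2.
- A reader might count the dosing blocks in 14 days and take that as the most drug in dispute. It is not a bound. The 14 days limit the time to recovery, not later dosing. A patient restarted at a persisting Grade 2 keeps receiving drug, while paragraph 2 holds with no time limit.
- A reader might infer that nothing covers Grade 2 stomatitis lasting beyond 14 days. Table 2 partly does, since it discontinues toxicity that stays clinically significant for more than 14 days. What is missing is a statement that this row applies here.

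**Conclusion.** The contradiction holds for Grade 3 stomatitis, both on the recovery grade and on the dose after a recurrence. This rests on the text alone and needs no assumption about event rates. It should be fixed because it sits in a safety instruction for a frequent toxicity and no other section resolves it.

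The statistical consequence is small and cannot be quantified from the protocol. It reaches the secondary tolerability outcome only when recovery falls on a conflicting path within the first 2 cycles and the investigator judges clinical benefit to be present. Nothing here supports a claim that the tolerability conclusion would be materially distorted, and the primary response outcome is unaffected.

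**What to change.** Rewrite 7.5.2.2 as one rule:

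- For Grade 2-3 stomatitis, restart only at Grade 1 or less: at the same dose after a first event, and one level lower (Table 1) on recurrence.
- Limit paragraphs 4 and 5 explicitly to Grade 4 events, or delete paragraph 4. Table 2 already discontinues Grade 3 toxicity that lasts beyond 14 days, so the limit leaves no hole there.
- State that Table 2's discontinuation row for clinically significant toxicity beyond 14 days applies to Grade 2 stomatitis that persists.
- Have the sponsor's clinicians confirm the recovery grade. If they want Grade 2 to suffice for benefiting patients, write that as a named exception and define clinical benefit.

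The cost is wording in one section, with no added data or visits. Keeping the Grade 1 threshold may produce slightly more holds, and so a slightly lower observed tolerability rate, than if sites used paragraph 4.
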